1.6.1 Analysis of safety

The percentage of subjects with at least one local AEs with at least one general AE (solicited and unsolicited) and with any AE during the 7-day or total follow-up period up to 28 days after the last vaccine dose and overall will be tabulated with exact 95% CI. The percentage of doses followed by at least one local AE (solicited and unsolicited), by at least one general AE (solicited and unsolicited) and by any AE during the 7-day or the total follow up period up to 28 days after the last vaccine will be tabulated with exact 95% CI. The same computations will be done for Grade 3 AEs, for any AEs considered related to vaccination and for any Grade 3 AEs considered related to vaccination.

The percentage of subjects reporting each individual solicited local AE (any grade and Grade 3) and solicited general AE (any grade, Grade 3, any related, Grade 3 related, resulting in medically attended visit) during the 7-day follow-up period (Day 0-6) after each vaccine dose and overall will be tabulated for each group. Similarly, the percentage of doses followed by each individual solicited local and general AE will be tabulated, overall vaccination course, with exact 95% CI.

For fever, the number and percentage of subjects reporting fever by half degree (°C) cumulative increments during the first seven days (Day 0-6) after each vaccine dose and overall will be tabulated. Similar tabulations will be performed for any fever with a causal relationship to vaccination and Grade 3 (> 39.5°C) causally related fever.

The percentage of subjects reporting unsolicited AEs from the date of the first vaccine dose up to 28 days after the last vaccine dose and after the sporozoite challenge will be tabulated by group and by MedDRA preferred term with exact 95% CI. Similar tabulation will be done for Grade 3 unsolicited AEs, for any causally related unsolicited AEs and for Grade 3 causally related unsolicited AEs.

The percentage of subjects reporting SAEs and pregnancies will be described in detail.

The percentage of vaccinated subjects reporting AEs of specific interest (meningitis and pIMDs) will be described in detail.

Research Proposal Submission Form for a study involving human subject enrollment WITH specimen collection

Document No.: FTM ECF-033-01

Page 46 of 52

Biochemistry (ALT, AST and creatinine) and haematological (haemoglobin, WBC and platelets) laboratory values will be presented according to toxicity grading scales and tabulated by group.

1.7 Holding rules and safety monitoring

No group holding rules will be pre-defined considering the evidence for a favourable safety profile of this candidate vaccine in Phase 2I infant evaluation.

Individual study participants who present with at least one of the following stopping rules will be withdrawn from further vaccine and/or drug administrations:

- Local reactions: upon investigator discretion.
- Systemic solicited adverse events: The subject develops a Grade 3 systemic solicited adverse event beginning within 2 days after vaccination/drug administration (day of vaccination and one subsequent day) and persisting at Grade 3 for >2 consecutive days.
- Unsolicited adverse events: The subject has any Grade 3 adverse event considered related to vaccination, persisting at Grade 3 for >2 consecutive days.
- The subject has a serious adverse event considered related to vaccination.
- The subject has an acute allergic reaction or anaphylactic shock following the administration of vaccine investigational product.
- Laboratory adverse events: The subject has any Grade 3 laboratory adverse event considered related to vaccination.

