Research Proposal Submission Form for a study involving human subject enrollment WITH specimen collection

Document No.: FTM ECF-033-01

Page 13 of 52

B5.5 Withdrawal/discontinuation criteria

Each participant has the right to withdraw from the study at any time and for any reason and is not obliged to give his or her reasons for doing so. Participants who are withdrawn because of AEs must be clearly distinguished from participants who are withdrawn for other reasons. For all withdrawals due to SAE/AEs, appropriate follow-up visits or medical care will be arranged, with the agreement of the participant, until the SAE/AE has resolved and stabilized

From an analysis perspective, a 'withdrawal' from the study is any participant who did not come back for the concluding visit or was not available for the concluding contact foreseen in the protocol. A participant qualifies as a 'withdrawal' from the study when no study procedure has occurred, no follow-up has been performed and no further information has been collected for this participant from the date of withdrawal/last contact. Investigators will make attempts to contact those participants who do not return for scheduled visits or follow-up.

In addition, participant may be withdrawn from the study by the investigator at any time, if it is in the best interests of the participant's health and well-being, or for any of the following reasons:

- Ineligibility (either arising during the study or retrospectively, having been overlooked at screening).
- Significant protocol deviation.
- Participant demonstrates significant non-compliance with study requirements
- An AE, which requires discontinuation of the study involvement or results in inability to continue to comply with study procedures.

If a participant withdraws from the study, blood samples collected before their withdrawal from the trial will be used/stored unless the participant specifically requests otherwise. Data collected prior to the withdrawal of a participant will be used. In all cases of participant withdrawal or discontinuation, excepting those of complete consent withdrawal, long-term safety data collection will continue as appropriate if subjects have received one or more vaccine doses.

Participant withdrawal from the study agent

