Document No.: FTM ECF-033-01

Page 23 of 52

be prepared by MORU statistician based on random numbers generated in STATA. The randomization sealed envelopes will be prepared by Clinical Trials Support Group (CTSG).

B6.4.4 Randomisation

Randomization numbers will be generated in blocks, for the 3 study arms in a ratio of 5:5:2, as follows:

- R21/Matrix-M™ + DHA-PIP+PQ (Arm 1)
- R21/Matrix-M™ alone (Arm 2)
- DHA-PIP+PQ alone (Arm 3)

Study participants will be assigned the next available randomization number on the list, and thus will be randomly allocated to Group 1, 2, or 3. This is an open-label study. Participants and clinical investigators will not be blinded to group allocation.

B6.4.5 First vaccination or anti-malarial medications initiation (Month 0 / Day 0 visit)

Participants in Group 1 and 2 will be vaccinated by intramuscular (IM) needle injection into the deltoid region of the arm. Participants in Group 1 will also receive anti-malarial medications. Participants in group 3 will receive anti-malarial medications only.

The study participants will be observed closely for at least 30 minutes following the administration of each study vaccine, with appropriate medical treatment readily available in case of an anaphylactic reaction.

An axillary thermometer, tape measure and a paper diary card for solicited AEs will be given to each participant along with the emergency 24-hour telephone number to contact the on-call study physician if needed. Diary cards will collect information on the timing and severity of the following solicited AEs (Table 8):

Table 8. Solicited AEs

Local solicited AEs	Systemic solicited AEs
Pain at injection site	Fever
Redness at injection site	Diarrhoea
Swelling at injection site	Nausea
Bruising at injection site	Vomiting
	Fatigue
	Headache
	Muscle pain (Myalgia)
	Joint pain (Arthralgia)
	Chills

Participants will be instructed on how to self-assess the severity of these AEs. There will also be space on the diary card to self-document unsolicited AEs, and whether medication was taken to relieve the symptoms.

**Research Proposal Submission Form
for a study involving human subject enrollment WITH
specimen collection**

Document No.: FTM ECF-033-01

Page 24 of 52

***B6.4.6 Subsequent vaccination (or subsequence rounds of anti-malarial medications) visits
(Month 1 / Day 0 and Month 2 / Day 0 visits)***

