1.5.2 Assessment of causality

The investigator will assess the relationship between investigational vaccines and study antimalarial medications and the occurrence of each AE/SAE. The investigator will use clinical judgment to determine the relationship. Alternative plausible causes, such as natural history of the underlying diseases, concomitant therapy, other risk factors, and the temporal relationship of the event to the investigational vaccines and study antimalarial medications will be considered and investigated. The investigator will also consult the IB and/or Summary of Product Characteristics to determine his/her assessment. There may be situations when a SAE has occurred and the investigator has minimal information. However, it is very important that the investigator always makes an assessment of causality. The investigator may change his/her opinion of causality in light of follow-up information and update the SAE information accordingly. The causality assessment is one of the criteria used when determining regulatory reporting requirements. In case of concomitant administration of vaccine and study antimalarial medication, it may not be possible to determine the causal relationship of general AEs to the individual vaccine or medication administered. All solicited local (injection site) reactions will be considered causally related to vaccination. Causality of all other AEs should be assessed by the investigator using the following question:

Research Proposal Submission Form for a study involving human subject enrollment WITH specimen collection

Document No.: FTM ECF-033-01

Page 44 of 52

Is there a reasonable possibility that the AE may have been caused by the investigational vaccine or study antimalarial medications?

- YES : There is a reasonable possibility that the vaccines or study antimalarial medications contributed to the AE.
- NO : There is no reasonable possibility that the AE is causally related to the administration of the study vaccines or study antimalarial medications. There are other, more likely causes and administration of the study vaccines and study antimalarial medications is not suspected to have contributed to the AE.

If an event meets the criteria to be determined as 'serious', additional examinations/tests will be performed by the investigator in order to determine ALL possible contributing factors for each SAE.

Possible contributing factors include:

- Medical history.
- Other medication.

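### Four of the six individual stopping rules in Appendix B 1.7 are tied to the vaccine, so drug-related events of those types in antimalarial-only Arm 3 trigger no mandatory stop

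*Protocol*

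**What the plan says.** Protocol Appendix B, 1.7 sets no group holding rules. It lists six rules for individuals and states that anyone who meets at least one "will be withdrawn from further vaccine and/or drug administrations". The consequence is therefore mandatory and extends to the drugs.

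Four of the six rules refer to the vaccine only:
- unsolicited events: "any Grade 3 adverse event considered related to vaccination, persisting at Grade 3 for >2 consecutive days";
- serious events: "The subject has a serious adverse event considered related to vaccination";
- allergy: "The subject has an acute allergic reaction or anaphylactic shock following the administration of vaccine investigational product";
- laboratory events: "The subject has any Grade 3 laboratory adverse event considered related to vaccination".

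Of the other two, local reactions are left to the investigator. The systemic solicited rule covers a Grade 3 event that starts within two days of vaccination or drug administration and stays at Grade 3 for more than two days.

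On treatment in Arm 3, B6.4.5 says: "Participants in group 3 will receive anti-malarial medications only". Under B6.2 these drugs are given in three rounds (Months 0, 1 and 2), with dihydroartemisinin-piperaquine on Days 0, 1 and 2 and primaquine on Day 0 of each round. The SAP contains no stopping rules.

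**The concern.** The consequence in 1.7 covers the drugs, but most of the triggers do not. Read exactly, 1.7 does not require dosing to stop in Arm 3 after a serious event caused by the antimalarials, or after anaphylaxis to one of them.

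This looks like an omission rather than a choice. The lead-in and the systemic solicited rule both mention the drugs, and the causality question in 1.5.2 asks about the vaccine or the study antimalarials. Drug-relatedness is thus assessed, yet no stopping rule uses it, and no reason is given.

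The gap also falls on effects that the protocol itself lists in C2.1. Dizziness (about 12%), abdominal pain and disturbed sleep are named for dihydroartemisinin-piperaquine, and none is on the solicited list in Table 8. A persistent Grade 3 case would fall under the unsolicited rule, which requires relation to vaccination. Haemolysis, the named primaquine risk, would show in laboratory values, and that rule has the same condition.

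What is at stake is the protection of healthy volunteers. No endpoint, analysis or sample size depends on it.

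**Working it through.** **1. Rules in 1.7, classified by trigger**

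| Rule | Trigger tied to | Mandatory | Reachable in Arm 3 |
|---|---|---|---|
| Local reactions | neither product | no, discretionary | by discretion only |
| Systemic solicited, Grade 3 | vaccine or drug | yes | yes |
| Unsolicited, Grade 3, persistent | vaccine | yes | no |
| Serious event | vaccine | yes | no |
| Allergy or anaphylaxis | vaccine product | yes | no |
| Laboratory, Grade 3 | vaccine | yes | no |

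Mandatory and reachable in Arm 3: 6 − 4 (vaccine-tied) − 1 (discretionary) = 1.

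**2. Arm 1**

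Arm 1 receives both products, so the gap is narrower. It applies to the unsolicited, serious and laboratory rules only when an event is attributed to the drugs and not to the vaccine. Section 1.5.2 warns that for general events "it may not be possible to determine the causal relationship of general AEs to the individual vaccine or medication administered".

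**3. Other provisions that might close the gap**

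- B5.5: "participant may be withdrawn from the study by the investigator at any time". Adverse events and ineligibility arising during the study are listed reasons, but under the same permissive wording.
- B5.7 is mandatory but stops R21/Matrix-M only.
- Sections 1.8.1 and 1.8.2 send all serious events to the Medical Monitor and the DSMB, who may recommend action. This is escalation and stops no individual's dosing.
- Table 5 marks the inclusion and exclusion criteria again at M1 D0 and M2 D0, although B5.2.2 says they are checked at study entry. Criterion 14 could catch a drug allergy, but the re-check is not marked at D1 or D2, so a Day 0 reaction would not reach it before the next two daily doses. For a drug-related serious event or a persistent Grade 3 unsolicited event, the re-check offers only criteria 2 and 13, both left to the investigator's judgement.
- Criterion 9 could catch some laboratory values. B6.6.1 lists eight at Day 7: Hb, WBC, platelets, ALT, AST, BUN, bilirubin and creatinine. Criterion 9 sets limits for five (Hb, platelets, AST, ALT, bilirubin), which leaves 8 − 5 = 3 without one (WBC, BUN, creatinine).

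So two of the four gaps (allergy and laboratory) are partly covered, and no other mandatory drug-stopping rule was found in either document.

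**4. How many participants**

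The documents give no rate for Grade 3 or serious drug events. The rates p below are assumptions, per Arm 3 participant, for the four event types together. With n = 20, the expected number is n × p and the chance of at least one is 1 − (1 − p)^n.

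| Assumed p | Expected number | Chance of at least one |
|---|---|---|
| 0.5% | 20 × 0.005 = 0.1 | 1 − 0.995^20 = 9.5% |
| 1% | 20 × 0.01 = 0.2 | 1 − 0.99^20 = 18.2% |
| 2% | 20 × 0.02 = 0.4 | 1 − 0.98^20 = 33.2% |

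These are chances that such an event occurs. Harm from the gap also requires that doses remain and that the drug is given again.

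**The case against.** The strongest reply is that this is a drafting slip with little practical effect.

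- **Frequent assessment.** Table 5 marks adverse events and withdrawal criteria for assessment at every visit after screening, including each dosing day, so withdrawal for an adverse event is actively considered in Arm 3. This is true and worth crediting, but those criteria lead back to the permissive wording of B5.5.
- **Judgement either way.** Relatedness is itself decided by the investigator, so for three of the four rules the rewording still rests on judgement. That stands in part. The difference is that once an event is judged drug-related, stopping would follow automatically. The allergy rule needs no relatedness judgement.
- **Loose reading of vaccination.** The protocol uses the day of vaccination to mean Day 0 in Arm 3, and the SAP safety table has a no-vaccine column for events timed by vaccine dose. The intent may therefore be broader than the words. But the text never says that relation to vaccination includes relation to the drugs, and the allergy rule names the vaccine product.
- **Criterion 10.** It refers to other abnormal blood tests and might cover the three values without limits. It is worded for screening and sets no limit of its own.
- **Oversight.** Serious events are escalated in every arm, whatever their cause. Non-serious events go to the Medical Monitor only if they meet pausing or halting criteria. With no group holding rules, those appear to be the 1.7 rules, so a non-serious Grade 3 drug event in Arm 3 may miss that step as well.
- **Low risk.** The protocol describes the combination as very well tolerated, the primaquine dose as safe even in severe G6PD deficiency, and the regimen as used in more than 10,000 people. A competent investigator would very probably stop the drug after anaphylaxis. This keeps the expected number small but does not correct the rule.

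**Conclusion.** The concern holds. One of the six rules is both mandatory and reachable in Arm 3, and four cannot be met there for a drug-related event. The finding is limited to explicit, mandatory rules: Arm 3 has discretionary protection, and an event that also meets the systemic solicited rule is covered. The count rests on the wording alone and needs no assumption. The size does: at assumed rates of 0.5% to 2%, fewer than one affected participant is expected, and the true number is unknown. The change should be made, because a stated safety rule gives the wrong result when followed literally. It does not threaten the validity of the trial's comparisons.

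**What to change.** In 1.7, change the unsolicited, serious-event and laboratory rules to read *related to vaccination or study antimalarial medication*. Change the allergy rule to name *vaccine or study antimalarial medication*. Add one sentence: *In Arm 1 the suspected product is stopped, or both if attribution cannot be separated.* Leave the timing window of the systemic solicited rule as it is, since B6.1 and B6.2 already use the day of vaccination for Day 0 in Arms 1 and 3.

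The cost is a wording amendment to four bullets plus one sentence, with no new visits or samples. The CRF is not among the documents, so whether it records the suspected product should be checked. There is one small downside. Where attribution cannot be separated, an Arm 1 participant may lose later vaccine doses and leave the per-protocol set, which requires three complete doses (protocol B6.7.4) and is the main set for immunogenicity (SAP 4.1.4). The added loss should be small, because an event judged possibly related to the vaccine already triggers the present rules.

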1.8 Safety Oversight

1.8.1 Medical Monitor

A Medical Monitor, representing the Sponsor, will be appointed for oversight of safety in this clinical study. The Medical Monitor will be responsible for safety assessments as outlined below. The monitor will review the study prior to initiation and will be available to advise the Investigators on study-related medical issues and to act as a representative for the welfare of the subjects. The monitor does not have direct involvement in the conduct of the study and does not have other interests with any collaborating pharmaceutical firms or their competitors. All serious adverse events and any AEs that fulfil the criteria for pausing or halting will be reported to the medical monitor within 24 hours of becoming aware of the event. The monitor is responsible for the review of the safety data and communication with the PI, and/or the Data Safety Monitoring Board (DSMB), as appropriate. The Medical Monitor may also provide recommendation for continuation, modification, or termination of the study, if there is urgent need.

1.8.2 Data and Safety Monitoring Board

The Data Safety Monitoring Board (DSMB) will review the study prior to initiation and review all SAEs at the end of the study. The Board may convene additional reviews if deemed necessary, on review of the safety data, as sent, periodically by the Medical Monitor. All SAEs will be reported

Research Proposal Submission Form for a study involving human subject enrollment WITH specimen collection

Document No.: FTM ECF-033-01

Page 47 of 52

by the PI to the DSMB at the same time they are submitted to the Institutional review board (IRB). The PI will notify the DSMB at the time pausing, or halting criteria are met, and obtain a recommendation concerning continuation, modification, or termination of the study. The PI will submit the written DSMB summary reports with recommendations to the IRB(s).

2 ADMINISTRATIVE INFORMATION

2.1 *Definition of Start and End of Trial*

The start of the trial is defined as the date of the first vaccination of the first participant. The end of trial is the date of the last visit of the last participant, which will be a maximum of 6 months after recruitment and first vaccination of the last participant.

2.2. *Ethics*

Ethical approval will be sought prior to commencing the study through the relevant Research Ethics Committees. Indemnity for the trial will be provided by the University of Oxford. SAEs will be reported to the medical monitor, DSMB, ethics committees and the Sponsor. GCP training will be provided to all staff/investigators who have no valid training certificate prior to commencing the studies.

2.3. *Declaration of Helsinki*

The Investigators at each site will ensure that this study is conducted in accordance with the principles of the Declaration of Helsinki.

2.4. *ICH Guidelines for Good Clinical Practice*

The trial will adhere to the Research Governance policies of the University of Oxford and the ICH GCP.

2.5. *Approvals*

The protocol, informed consent form, participant information sheet, and other written participant information / materials will be submitted to appropriate Research Ethics Committees (RECs), and regulatory authorities for written approval. The Principal Investigator will submit and, where necessary, obtain approval from the above parties for all amendments to the original approved documents.

2.6. *Participant Confidentiality*

The trial staff will ensure that the participants' anonymity is maintained. The participants will be identified only by participants' ID number on the CRF and in any electronic databases. All documents will be stored securely and only accessible to trial staff and authorized personnel. Only the sponsor representative, investigators, the clinical monitor, authorized individuals from the, Jenner Institute, the ethical committee(s) and the regulatory authorities will have access to the

Research Proposal Submission Form for a study involving human subject enrollment WITH specimen collection

Document No.: FTM ECF-033-01

Page 48 of 52

records. Data will be anonymized as soon as it is practical to do so. With subject's consent, subject's clinical data and results from blood analyses stored in our database may be shared with the Jenner Institute and other researchers in the future. However, the other researchers will not be given any information that could identify the subject.

